## 10.9 Toxicity Management

All patients should have blood drawn for laboratory abnormalities assessment before any administration of IMP. Blood draws prior to IMP administration should be tested in the local laboratory.

Management of patients with a DLT within a given dose-escalation cohort: Patients who experience a DLT within a given cohort will be monitored by the Investigator until resolution and the Investigator will report the occurrence of a DLT without any delay or within 24 hours of knowledge or occurrence of the event to Transgene and Transgene representative.

If a patient death occurs within 28 days of the last Pexa-Vec or nivolumab administration due to a serious and unexpected Adverse Drug Reaction (ADR) that is determined by the Investigator or Transgene Medical Monitor to be possibly or probably related to Pexa-Vec and/or nivolumab, further administration of Pexa-Vec /nivolumab will be suspended for ongoing patients. Additionally, further patient enrolment into the study will be suspended and ISC, Ethics Committees (ECs) and Regulatory Authorities will be notified as regards further study handling.

• Management of Adverse Events (other than the formation of pustules)

Patient Management: in case of grade 3 or 4 adverse events considered as related to Pexa-Vec and/or nivolumab, the Investigator should contact Transgene Medical Monitor regarding the management of the patient and to determine if the next administration of Pexa-Vec or nivolumab should be postponed until resolution within an acceptable timeframe (*i.e.* within 30 days) otherwise the Pexa-Vec and/or nivolumab treatment will be stopped (*i.e.* no subsequent injection or infusion, respectively).

• Overall Management in the event of Pustule Formation

Pustule Management: specific precautions should be applied to patients treated with Pexa-Vec, in whom the occurrence of pustules is observed, to prevent contamination from spread of the virus in the environment:

- The infusion sites and any skin lesions should be covered loosely with a non-occlusive bandage (e.g., gauze) held in place with first-aid tape for at least 1 week after treatment. If a blister forms, bandaging of the infusion sites or skin lesions should be continued either until healed or the scab falls off.

- Non-occlusive bandage should be changed at least every 3 days or every time the bandage becomes wet.
- Infectious wastes should be disposed of according to the Institution or local procedures.
- Contaminated linen should be managed according to the Institution or local procedures.
- Recommendation to wear personal protective equipment when changing the bandage on the injection/infusion sites and skin lesions, to remove the gloves and clean hands immediately after changing the bandage and before touching any other part of the patient's body, another person, or objects in the environment.

Patient Management: in the event that the AE is due to skin lesions  $\geq$  than 10 pustules corresponding to infection that is possibly or probably related to the administration of Pexa-Vec, the Investigator will contact Transgene and a patient monitoring plan will be implemented to fully document the occurrence and evolution of the pustules (e.g. photographs of skin lesions). Specific details and instructions will be provided to Investigators as part of a patient monitoring plan and other site-specific study documentation. Transgene must be notified immediately and the ISC may be consulted as needed.

Management in the event of suspected infectious complication related to Pexa-Vec

In case of occurrence of symptoms compatible with the development of an infectious complication that may be related to Pexa-Vec, such as described in paragraph 10.1, please contact Transgene Medical Monitor.

For France, management guidelines have been established by the Société de Pathologie Infectieuse de Langue Française (SPILF), Coordination Opérationnelle du Risque Epidémique et Biologique (COREB) and are described in Appendix 4: Procédure SPILF – COREB – Vaccine.

Management in the event of accidental exposure to Pexa-Vec

Any accidental exposure should be reported to Transgene's representative within 24 hours of occurrence or knowledge of occurrence, and documented and followed-up using an "Report of Exposure to Infectious Material", faxed to the below number.

For France, the SPILF-COREB has established management guidelines which are to be followed by French sites (Appendix 4).

Management of Laboratory Abnormalities

[figure not shown]
All clinically significant laboratory abnormalities of Grade 3 or 4 and regardless of the relationship to the IMP should be confirmed by repeat testing within up to 5 days of

receipt of results. If the laboratory abnormality is confirmed and considered at least possibly related to Pexa-Vec and/or nivolumab, the Investigator should contact the Coordinating Investigator (SC) regarding the management of the patient and to determine if the treatment regimen can be reinitiated once the laboratory abnormality has resolved.

If the laboratory abnormality considered at least possibly related to Pexa-Vec and/or nivolumab has not resolved, the next administration should be postponed until resolution within an acceptable timeframe (*i.e.* within 30 days) otherwise the Pexa-Vec and/or nivolumab treatment will be stopped (*i.e.* no subsequent dosing).

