#### Safety and clinical assessments

tMP1 (Investigational Medicinal Product): Nivolumab, programmed death receptor-1 (PD-1) blocking antibody (Opdivo\* - BMS)

IMP2: Pexastimogene devacirence, Vaccinia GMCSF / Thymidine

Clinical Protocol: TG5006.01

EndraCT N° 2016-000085-32 IND N° 17439

1MP2: Pexastimogene devacirepvec, Vaccinia GMCSF / Thymrdin Kinase-Deactivated Virus (Pexa-Vec-, JX594, TG6006 - Transgene)

- Physical examination including vital signs, body weight and Performance Status measurements will be performed at each visit.
- Adverse Events and Serious Adverse Events (SAEs) will be reported and graded according to National Cancer Institute's Common Toxicity Criteria for Adverse Events (NCI CTCAE), version 4.03
- Safety laboratory investigations will be undertaken at baseline, every 2 weeks during the 6 first weeks and then every 6 weeks, at the end of treatment visit and at the safety follow-up visit:
  - Complete blood cells count
  - Biochemistry analyses (including: AST, ALT, alkaline phosphatases, total bilirubin, LDH, serum protein, serum albumin, electrolytes), CRP and creatinine
- Monitoring for cardiac toxicity will include for both phases of the study:
  - Cardiac echography (ECHO) with measurement of left ventricular ejection fraction (LVEF), if necessary, in addition to baseline measurement,
  - Measurement of troponin T or I blood level 3 and 8 days (± 1) after each Pexa-Vec administration.
  - ECG (12 leads), 8 days (± 1) after each Pexa-Vec administration,
  - ECG (12 leads), 3 days (± 1) after each Pexa-Vec administration, in case of detection of a clinically significant increase in troponin blood level,
  - In the Phase I section, measurement of troponin T or I level will be performed at D29 (end of DLT period), then starting from week 8, ECHO, ECG and troponin T or I level will be performed every 4 weeks (i.e. on every second nivolumab infusion) up to the 28-day safety follow-up visit.

Further examination(s) will be performed if deemed necessary by the investigator.

- Antinuclear and anti-TPO antibodies at baseline and at the end of treatment visit
- Thyroid blood tests will be performed at baseline and every 6 weeks, at the end of treatment visit and at the safety follow-up visit
- Alpha-feto protein (AFP) blood concentration at baseline and at the end of treatment visit

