# 1.6 Potential risks and benefits associated with nivolumab

The overall safety experience with nivolumab is based on experience in approximately 8,600 subjects as either monotherapy or in combination with other therapeutics. In general, for the monotherapy, the safety profile is similar across tumor types. The most frequently reported treatment-related AE is fatigue, which is almost always of low grade. Most related AEs are thought to be due to the effects of inflammatory cells on specific tissues.

In several ongoing clinical trials, the safety of nivolumab in combination with other therapeutics such as ipilimumab, cytotoxic chemotherapy, anti-angiogenics, and targeted therapies is being explored. Most studies are ongoing and, as such, the safety profile of nivolumab combinations continues to evolve.

Hepatic AEs, including elevated liver function tests (LFTs) and, infrequently, drug-induced liver injury (DILI), have been observed following treatment with nivolumab. Most cases were of low or moderate grade. Higher-grade hepatic AEs, including DILI, were managed with corticosteroids (with or without mycophenolate mofetil) and, in almost all cases, the events resolved. The recommended management of hepatic AEs is provided in Appendix 3. Early recognition and treatment of elevated LFTs and DILI are critical to their management. Subjects should be advised to seek medical evaluation if they notice jaundice (yellow appearance of skin

or sclera) or if they develop bruising, bleeding, or right-sided abdominal pain. Physicians should monitor LFTs prior to each nivolumab treatment. As LFT abnormalities are common in subjects with HCC, it is important that an evaluation/work-up distinguishes between non-drug-related causes (e.g., infection, progression of disease, concomitant medications, or alcohol) and a possible drug-related AE as the management can be quite different. The principal treatment for high-grade hepatic AEs is corticosteroids. Consultation with Transgene medical monitor should be sought for all moderate- and high-grade hepatic AEs.

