- Blood sample collection for the following testing: hematology, chemistry, coagulation and CRP
- Pregnancy test (urine) for WOCBP (if positive, an ultrasound will be performed to confirm pregnancy)
- Ultrasound scan may be optionally performed to assess suitability of IT injection within selected liver lesions and to select lesions for injection
- Nivolumab infusion 1
- Pexa-Vec intratumoral injection 2
- In case the administrations are distributed over 2 consecutive days, patients will undergo another complete physical examination and recording of vital signs prior to Pexa-Vec administration on the second treatment day.

Patients will be observed in the clinic or hospital for a minimum of 8 hours after IT Pexa-Vec treatment. After injection, the following procedures will be implemented:

- Reporting of AEs (that occurred during or after either drug administration) and concomitant medications.
- Vital signs (blood pressure, temperature, heart and respiratory rates) 15 minutes (±5 minutes) after injection completion and then every hour (±15 minutes) for at least 8 hours after Pexa-Vec treatment, after which monitoring will be performed every 6 hours up to 24 hours or patient's release from hospital.

Patients will be monitored for troponin T or I blood level 3 and 8 days  $(\pm 1)$  after Pexa-Vec administration.

Patients will undergo an ECG 8 days (± 1) after Pexa-Vec administration.

Patients will undergo an ECG 3 days ( $\pm$  1) after Pexa-Vec administration, in case of troponin clinically significant increase.

## 8.6 Day 29 visit (± 1 day): nivolumab infusion 2 - Pexa-Vec injection 3

Before Day 29 nivolumab infusion and intratumoral injection of Pexa-Vec, patients will undergo:

- Complete physical examination, including weight, vital signs, and ECOG PS
- Skin and mucosal examination; AEs and concomitant medications reporting
- Blood sample collection for the following testing: hematology, chemistry, coagulation and CRP
- Pregnancy test (urine) for WOCBP (if positive, an ultrasound will be performed to confirm pregnancy)
- Ultrasound scan may be optionally performed to assess suitability of IT injection within selected liver lesions and to select lesions for injection
- Nivolumab infusion 2
- Pexa-Vec intratumoral injection 3
- In case the administrations are distributed over 2 consecutive days, patients will undergo another complete physical examination and recording of vital signs prior to Pexa-Vec administration on the second treatment day.

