# 8.7 Radiographic Status Visits: Week 6 ±2 Days and every 6 weeks ±4 Days

At Week 6, radiographic status will be evaluated and then every 6 weeks  $\pm 4$  days up to the End of Treatment Visit.

Beyond 12 months of treatment, the evaluations will be performed every  $12 \pm 2$  weeks until documented progression or discontinuation of treatment beyond progression. If study treatments are stopped before documented radiological progression, PFS visits will be performed every 6 weeks to continue radiological assessment until documented progression. Patients will complete the following procedures:

- Complete physical examination, including weight, vital signs, and ECOG PS
- Skin and mucosal examination; AEs and concomitant medications reporting
- Blood sample collection for the following testing: hematology, chemistry, coagulation, CRP and thyroid blood tests
- Pregnancy test (urine) for WOCBP (if positive, an ultrasound will be performed to confirm pregnancy)
- Tumor assessment: CT or MRI, according to screening assessment
- Patient contact log update
- Week 6 only:
  - o HBV and HCV viral load

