# 8.8 Nivolumab infusion Visits: Week $6 \pm 2$ Days and every 2 weeks $\pm 4$ Days

Nivolumab infusion visits will be planned every 2 weeks (± 2 days), at which patients will complete the following procedures:

- Complete physical examination, including weight, vital signs, and ECOG PS
- Skin and mucosal examination; AEs and concomitant medications reporting.

In addition, in the **phase I** part of the study, the following assessments will be performed every 4 weeks starting on Week 8:

- 12-lead ECG
- Cardiac echography (ECHO) with measurement of LVEF
- Measurement of troponin T or I level.

At week 6 and after Week 6, radiographic status visits (q6 weeks) will be combined with nivolumab infusion visits (q2 weeks), should nivolumab treatment continuation be appropriate.

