# FLOW-CHART

Long- term follow up (up to 5	Yearly after last study visit			×			×									
follow up	q8 weeks (± 7 days)															
28-day safety follow-up End of study Visit**	≥28 days after last IMP intake and PD		_		×		×		×	×	×	×	×	×	×	
PFS follow -up Visit	q6 weeks until PD						×		×	×	81					
End of treatment Visit	After treatment discont. with or w/o PD		:0		×		×		×	×	×	×	×	×	×	
Pexa- Vec Boost Visit	≥ W12				×		×		×	×	×	×	×	×		
Radio- graphic Status Visits	q6 weeks (± 4 D)		n.		×		×		×	×	×	×	×	×	×	
Subsequent Nivolumab Cycles	q2 weeks (± 4 Days)				×		×		×	×						
Radio- graphic Status Visit 1	W6 (±2D)				×		×		×	×	×	×	×	×	×	
Pexa-Vec IT 3 Nivo IV 2	Day 29 (± 1 D)				×		υX		υX	×	×	×	×	×		
Pexa-Vec IT 2 Nivo IV 1	Day 15 (± 1 D)		id.		×		Χu	7.65	υ×	×	×	×	×	×		
Fexa-Vec IT 1	Day 1			×	×		×		×	×						
Baseline	Days -4 to -1			×	×	Ϋ́P	×		×	×	×	×	×	×	×	
screening	Days -28 to -2ª	×	×		×	×	×	×	×	X	×	×	×	×		×
Schedule of Activities	Day/Week (Window)	Signature of ICF	Medical, surgical and cancer histories and demographic information	Medical history update	Prior and Concomitant medications	Review of inclusion and exclusion criteria	Complete physical examination, including weight	Height	Vital signs c	ECOG performance status	Hematology	Serum chemistry d	Coagulation (aPTT, INR)	C-reactive protein	Thyroid blood tests	HIV/HBV/HCV

Transgene / Confidential Amended Version – March 20, 2019

Study Protocol TG6006.01

	T T		$\neg$		1					$\overline{}$	$\overline{}$	1	1				$\overline{}$						
Long- term follow up (up to 5	Yearly after last study	visit																					
follow qu	q8 weeks (± 7 days)																						
28-day safety follow-up End of study Visit m	≥28 days after last IMP intake and PD									×					×				>	<			
PFS follow -up Visit	q6 weeks until PD																						
End of treatment Visit	After treatment discont.	W/0 PD	< ×	×										×									
Pexa- Vec Boost Visit	≥ W12									×				×		€							
Kadio- graphic Status Visits	q6 weeks (± 4 D)									×				×									
Subsequent Nivolumab Cycles	q2 weeks (± 4 Days)													×	°×				, Xo	4			
Radio- graphic Status Visit 1	W6 (± 2 D)					×	×	}		×				×									
Pexa-Vec IT 3 Nivo IV 2	Day 29 (±10)									×				×	D29 &	D37 (±1D)	(D32)	(±1D)	*	:			
Fexa-vec IT 2 Nivo IV 1	Day 15 (± 1 D)									×				×	(D23)	(± 1 D)	(D18)	(± 1 D)					
rexa-vec	Day 1													×	(D9)	(± 1 D)	(D4)	(± 1 D)					
	Days -4 to -1			×	×	×	×			×					×				×	:		×	÷

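### Protocol 1.6 and 10.9 ask for liver tests or bloods before each nivolumab dose, but the visit schedule provides none at infusion visits between the 6-weekly radiographic visits

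*Protocol*

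**What the plan says.** **Text asking for tests before each dose**

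- Protocol 10.9: "All patients should have blood drawn for laboratory abnormalities assessment before any administration of IMP". It adds that these samples go to the local laboratory. Nivolumab and Pexa-Vec are both IMPs (Protocol 5).
- Protocol 1.6: "Physicians should monitor LFTs prior to each nivolumab treatment".
- Protocol 6.3.4.2 asks for laboratory values to be reviewed around each infusion. On its own this does not call for a new sample.

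**Text setting the schedule**

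- Synopsis, safety assessments: laboratory tests are done at baseline, "every 2 weeks during the 6 first weeks and then every 6 weeks", and at the end-of-treatment and safety follow-up visits.
- Protocol 8.8: "Nivolumab infusion visits will be planned every 2 weeks (± 2 days), at which patients will complete the following procedures". The list that follows covers examination, weight, vital signs, ECOG, skin and mucosa, adverse events and concomitant medications. In Phase I it adds ECG, echocardiography and troponin every 4 weeks from Week 8. It contains no haematology or chemistry.
- Appendix 1: the column headed "Subsequent Nivolumab Cycles" is marked for concomitant medications, examination, vital signs and ECOG, and is blank for haematology and chemistry.

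**Visits that do list bloods**

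- Protocol 8.5 and 8.6 (Days 15 and 29): "Blood sample collection for the following testing: hematology, chemistry, coagulation and CRP".
- Protocol 8.7 (radiographic visits): "Blood sample collection for the following testing: hematology, chemistry, coagulation, CRP and thyroid blood tests".
- Protocol 8.9 (boost visits) lists the same panel as Days 15 and 29.
- Protocol 8.8 links the two schedules: "At week 6 and after Week 6, radiographic status visits (q6 weeks) will be combined with nivolumab infusion visits (q2 weeks"). Every third infusion visit therefore carries the 8.7 bloods.

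**The concern.** The per-dose text and the visit schedule give sites different instructions, and nothing says which prevails. Bloods are listed explicitly at most other dosing visits. Section 8.8 even names one blood test, troponin in Phase I, without naming chemistry. A coordinator working from the flow-chart could fairly take the blank cells as intended, and the synopsis supports that reading.

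What is at stake is patient safety. Permanent discontinuation under 6.3.4.2 depends on laboratory values:

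- drug-related AST or ALT above 8×ULN;
- total bilirubin above 5×ULN;
- AST or ALT above 3×ULN together with bilirubin above 2×ULN;
- Grade 3 thrombocytopenia that lasts more than 7 days or comes with bleeding.

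Protocol 1.7 names rises in AST, ALT and bilirubin as anticipated effects of the combination. Protocol 1.4.1.1.2 reports nivolumab-related Grade 3 AST increase in 11% and ALT increase in 9% of patients with HCC. A site following the visit list could give an infusion without current values for these criteria.

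**Working it through.** The plan states no figure for this point, so the check compares two schedules and counts.

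**Inputs**

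- Nivolumab every 2 weeks from Day 15, that is Weeks 2, 4, 6, ... (Protocol 6.1.2.2).
- Scheduled haematology and chemistry on treatment: Day 15 (Week 2), Day 29 (Week 4), Week 6, then every 6 weeks (synopsis, 8.5 to 8.7).
- Horizon: Week 52. Assumptions: nominal visit dates, no interruption, no boosts.

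**Step 1: infusions after Week 6.** Weeks 8, 10, ..., 52: (52 − 8)/2 + 1 = 23.

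**Step 2: infusions with scheduled bloods.** Weeks 12, 18, 24, 30, 36, 42, 48: 7.

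**Step 3: infusions without.** 23 − 7 = 16, and 16/23 = 69.6%.

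**Step 4: age of the latest scheduled value at those 16.**

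| Nominal age | Weeks | Count |
|---|---|---|
| 2 weeks | 8, 14, 20, 26, 32, 38, 44, 50 | 8 |
| 4 weeks | 10, 16, 22, 28, 34, 40, 46, 52 | 8 |

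**Step 5: overlap with Phase I troponin.** Troponin is drawn every 4 weeks from Week 8. Of the 16 infusions, Weeks 8, 16, 20, 28, 32, 40, 44 and 52 include that draw: 8 visits.

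**Step 6: room between entry limits and stopping limits.** Inclusion criterion 9 allows AST or ALT up to 5×ULN, bilirubin up to 1.5×ULN and platelets from 60×10⁹/L.

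- From AST 5×ULN, the 8×ULN limit is a 1.6-fold rise away (8/5).
- From bilirubin 1.5×ULN with AST above 3×ULN, the combined criterion is a 1.33-fold bilirubin rise away (2/1.5).
- Grade 3 platelets begin below 50×10⁹/L (SAP Appendix 1).

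Step 6 shows that an eligible patient can start near a limit. It does not estimate how often a limit is crossed.

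**Not counted.** The 3-weekly nivolumab option and treatment beyond 12 months are left out because the documents do not fix when bloods would fall. After 12 months, 8.7 moves radiographic visits to every 12 weeks while the synopsis keeps laboratory tests 6-weekly.

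**The case against.** **Existing rules cover known problems.** Protocol 10.7 has clinically relevant abnormal results repeated at once and followed. Protocol 10.9 has clinically significant Grade 3 or 4 abnormalities retested within 5 days, and postpones the next dose if the abnormality is related and unresolved. Appendix 3 requires immediate liver tests, reviewed before the next dose, when symptoms suggest hepatitis. A patient with a known abnormality or symptoms therefore leaves the 6-weekly rhythm. This stands, and it narrows the exposure to new, asymptomatic changes between scheduled draws.

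**A blank column is not in itself a contradiction of 10.9.** Day 1 is an IMP dose with no haematology or chemistry at the visit. Screening and baseline samples serve it, and Protocol 8.2 says results must be in hand before Day 1. Section 10.9 does not say how recent the sample must be and names no panel. This stands in part: the clearest per-dose duty is in 1.6, which covers LFTs only. It does not remove the conflict between 1.6 and the schedule.

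**The wording is softer than a rule.** Sections 1.6 and 10.9 say what should be done, and a site may draw the samples anyway. That is true, but the schedule neither prompts nor plans it.

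**The count is of visits, not harm.** The 11% and 9% figures carry no onset times, so the documents cannot show how many rises would begin after Week 8 or fall between draws. This stands.

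**Appendix 3 is only partly legible.** The body of its hepatotoxicity table is not in the public text, so what it asks once tests change cannot be fully judged. Its call for periodic testing fits either reading and does not settle the matter.

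**Conclusion.** The mismatch is real and should be fixed. With 2-weekly dosing to Week 52, no interruptions and no boosts, up to 16 of 23 infusions (70%) from Week 8 have no scheduled haematology or chemistry. The latest scheduled value is nominally 2 weeks old at half of them and 4 weeks old at the other half. This is a maximum, since patients who stop earlier have fewer such infusions. The residual risk is a new asymptomatic rise in AST, ALT or bilirubin, or a fall in platelets, that would meet a 6.3.4.2 criterion but is not measured before the next dose.

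Three stronger readings might be inferred, and the documents do not support them:

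- *Laboratory monitoring is absent after Week 6.* It continues every 6 weeks, with follow-up of known abnormalities and symptom-triggered liver tests.
- *70% of infusions are unsafe.* The figure describes the schedule. No onset data are given from which to estimate missed events.
- *The DLT assessment or the ORR result is compromised.* Bloods are scheduled on Days 15 and 29, within the DLT period, and ORR rests on imaging.

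**What to change.** Make additions only, leaving present tests in place:

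1. **Protocol 8.8 and the nivolumab-cycle column of Appendix 1:** add locally tested serum chemistry, including AST, ALT and total bilirubin, with haematology for the platelet criterion, reviewed before dosing at every infusion visit.
2. **Synopsis:** add a test before each nivolumab infusion, keeping the 6-weekly, end-of-treatment and safety follow-up tests.
3. **Appendix 3, hepatotoxicity:** keep periodic testing during treatment and add a test before each nivolumab infusion.

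Replacing the periodic wording in items 2 and 3 would be a mistake. Nivolumab may be held for up to 42 days from the last dose for toxicity, and longer during a steroid taper (6.3.4.2). Under wording tied only to infusions, those texts would call for no tests during a hold.

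Including haematology is a choice: 1.6 names only LFTs and 10.9 specifies no panel. The platelet stopping criterion is the reason for it.

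**Result:** all 23 infusions from Week 8 to Week 52 would have scheduled values, against 7 now.

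**Cost:** wording in four places and up to 16 more scheduled draws per patient through Week 52, at visits already taking place. In Phase I, 8 of those 16 visits already include a troponin draw.
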